3.2.1.2 Study doses and control groups

Patients must be on a stable treatment of at least 30 IU of insulin per day, with or without OADs for 8 weeks to be eligible for enrolment in this trial. Patients on metformin therapy should be on at least 1500 mg/day of metformin or at the maximum tolerable dose for a period of at least 8 weeks prior to enrolment. Patients on other OAD medications should be on at least half maximum daily recommended dose of the OAD for a period of at least 8 weeks prior to enrolment. Patients with at least 30 IU calculated mean daily insulin dose will be randomized at visit 2 if the daily insulin requirements over the past seven days with insulin use documentation does not vary more than 10% of the calculated mean daily insulin dose. To ensure approximate balance across treatment groups within each stratum (patients with additional OADs and patients without additional OADs) the randomisation will be performed in two strata: one for patients with OADs and one for patients without OADs. Eligible patients will be randomized in a 1:1:1:1 ratio to receive either dapagliflozin at 2.5 mg, 5 mg, 10 mg or placebo once daily. During the study treatment the patients will be instructed to keep their insulin (and if applicable OAD) dose unchanged. Patient will be instructed to record their fasting SMBG and insulin use daily. Patient will further be instructed to always self-monitor plasma glucose in case of symptoms suggestive of hypoglycaemia and to register any signs of hypoglycaemia in the supplied diary. The dapagliflozin doses 2.5 mg, 5 mg, and 10 mg/day were chosen for the Phase III program based on efficacy, pharmacodynamic, and safety data from the Phase I and Phase II programs. This dose range is supported by the following assessments:

- In the Phase I and IIa program, maximal glucosuria was seen at the 10 to 20 mg dose level. Doses ≥ 20 mg only increased the duration of glucosuria. In the Phase IIb study (MB102008), glucosuria appeared related to dose, with maximal glucosuria seen at the 20 and 50 mg doses.
- In the Phase IIb study (MB102008), dapagliflozin improved glycaemic parameters throughout the dose range of 2.5 mg to 50 mg daily, with most of the efficacy realized within the dose range of 2.5 mg to 10 mg. There was no apparent dose relationship beyond 10 mg for HbA1c or for PPG AUC, though there was evidence for a continued dose-response relationship up to 50 mg with respect to FPG.
- In the Phase IIb study (MB102008), weight loss was seen at all doses, with an apparent relationship to dose.
- In the Phase IIb study (MB102008) genitourinary infections were more common in the 20 and 50 mg dose groups.
- In the Phase IIb study (MB102008) an increase in haematocrit was seen at all doses, with an apparent relationship to dose, and a step-up seen at doses greater than 10 mg.
- In the Phase IIb study (MB102008) the incidence of the marked laboratory abnormality of hyperphosphataemia was higher than for placebo at doses of 20 and 50 mg dapagliflozin.

Based on the data from the Phase IIb trial, doses greater than 10 mg increase the potential risks of fluid losses, increased hematocrit and hyperphosphatemia, without the promise of substantially greater glycaemic efficacy.

3.2.1.3 Choice of outcome variables

In the regulatory guidelines for type 2 diabetes ([CPMP 2002](#)), HbA1c is the variable of choice for determination of glycaemic control and was therefore chosen as the primary variable. Dapagliflozin as an agent that inhibits renal tubular glucose re-absorption may have an additive glucose lowering effect when given in combination with another anti-diabetic drug. Positive effect on HbA1c, weight and Fasting Plasma Glucose as well as reduction in insulin dose may be expected. The reduction of HbA1c is therefore chosen as a primary efficacy endpoint whereas reduction of body weight, mean daily insulin dose reduction and FPG are chosen as important secondary efficacy endpoints in part to characterise the dapagliflozin therapy.

Other measures are assessed in this protocol to better understand the mechanistic and pharmacodynamic effects of dapagliflozin. In particular, these include other secondary efficacy outcome variables of change in glycaemic parameters, seated systolic and diastolic blood pressure, and lipids.

3.2.1.4 Choice of study population

The study population was selected to balance demands on representation of the future patient population and limit bias caused by confounding factors. The prevalence of type 2 diabetes increases with age and therefore the study will include also elderly patients up to 80 years of age. Women are not allowed to be or to become pregnant or breast feeding since dapagliflozin has not been tested in pregnant or breast feeding women and the risk to the embryo, foetus, or infant are unknown.

The HbA1c entry criterion was selected to permit patients with a wide range of glycaemic levels. The HbA1c interval of $\geq 7.5\%$ and $\leq 10.5\%$ reflects inadequate glycaemic control and is chosen in order to exclude patients who could easily be treated to normoglycaemia by slightly optimising insulin dose. Continuously evolving treatment guidelines such as the International Diabetes Federation Global Guideline for type 2 diabetes 2005 (**International Diabetes Federation 2005**), The National Institute for Clinical Excellence Guideline Management of type 2 diabetes – Management of Blood Glucose (**National Institute for Clinical Excellence 2002**), American Diabetes Association Position Statement on Standard of Medical Care in Diabetes 2006 (**American Diabetes Association 2006**), and the American Association of Clinical Endocrinologist Medical guidelines for the management of diabetes mellitus (**American Association of Clinical Endocrinologists 2007**) suggest HbA1c level $< 6.5\%$ for optimal glycaemic control. Although individual guidelines recommend treatment to normal HbA1c levels (e.g. $< 6.1\%$), the risk of hypoglycaemia may limit the possibility to achieve this in clinical practice. The purpose of the remaining inclusion and exclusion criteria is to limit confounding factors that would complicate the interpretation of the results (eg corticosteroid-induced type 2 diabetes, haemoglobinopathies that would interfere with the HbA1c analyses) or to exclude patients whose safety could be compromised by participation in the study.

3.2.2 Risk/benefit and ethical assessment

In a Phase 2b study all doses of dapagliflozin were associated with a statistically significant and clinically relevant improvement in glycaemic control and relatively minor AE's and effects upon fluid/electrolyte status. The safety data collected to date from clinical studies in healthy volunteers and subjects with T2DM indicate that the clinical safety profile of dapagliflozin supports proceeding with Phase 3 studies at doses of 2.5 mg, 5 mg and 10 mg per day. Evaluation of the clinical safety and clinical efficacy data accumulated so far indicate an acceptable risk/benefit profile at these planned doses. The long-term safety profile of dapagliflozin is not currently known.

For further information please refer to Clinical Study Protocol [Appendix I - Overall Benefit and Risk Assessment](#).

The planned switch of patients randomised to the dapagliflozin 5 mg treatment arm to dapagliflozin 10 mg during long term extension period II will have no influence on the above risk-benefit assessment.

3.3 Selection of study population

3.3.1 Study selection record

Investigator(s) must keep a record of subjects who were considered for enrolment but were never enrolled eg subject screening log. This information is necessary to establish that the subject population was selected without bias.

3.3.2 Inclusion criteria

For inclusion in the study subjects must fulfil all of the following criteria:

Inclusion criteria at enrolment (visit 1):

1. Provision of a written informed consent
2. Men and women diagnosed with type 2 diabetes
3. Age ≥ 18 - ≤ 80 years at time of consenting
4. Patients with inadequate glycaemic control, defined as HbA1c $\geq 7.5\%$ and $\leq 10.5\%$, and who, according to investigators judgement, are on a stable insulin regimen, with a mean dose of at least 30 IU of injectable insulin per day, for a period of at least 8 weeks prior to enrolment. Patients may also be treated with maximally two OADs under the approved prescribing information. OAD treatment should be at a stable dose for a period of at least 8 weeks.

Patients on metformin therapy should be on at least 1500 mg/day of metformin or at the maximum tolerable dose for a period of at least 8 weeks prior to enrolment. Patients on other OAD medications should be on at least half maximum daily recommended dose of the OAD for a period of at least 8 weeks prior to enrolment.

Inclusion criteria before randomisation (visit 2):

1. Patients with HbA1c $\geq 7.5\%$ and $\leq 10.5\%$ according central laboratory values measured from sample taken at visit 1 and who are on a stable insulin regimen with a mean insulin dose of least 30 IU of injectable insulin per day either without any other OADs or with a stable dose of OADs that have been approved in combination with insulin.
2. Daily insulin requirements over the past seven days with insulin dose documentation that does not vary more than 10% on more than one occasion of the calculated mean daily insulin dose at visit two (For example for patient whose calculated mean daily insulin dose at visit 2 is 50 IU, daily doses in the preceding seven days with insulin dose documentation may not be <45 and >55 IU on more than one occasion).

3. Women of childbearing potential (WOCBP) must be using an adequate method of contraception to avoid pregnancy throughout the study and for up to 4 weeks after the study in such manner that the risk of pregnancy is minimized and must have a negative serum or urine pregnancy test (minimum sensitivity 25 IU/L or equivalent units of HCG) within 72 hours prior to the start of study medication. WOCBP include any female who has experienced menarche and who has not undergone successful surgical sterilization (hysterectomy, bilateral tubal ligation or bilateral oophorectomy) or is not postmenopausal (defined as amenorrhea ≥ 12 consecutive months; or women on hormone replacement therapy (HRT) with documented serum follicle stimulating hormone (FSH) level >35 mIU/mL). Even women who are using oral, implanted or injectable contraceptive hormones or mechanical products such as an intrauterine device or barrier methods (diaphragm, condoms, spermicides) to prevent pregnancy or practicing abstinence or where the partner is sterile (eg vasectomy), should be considered to be of child bearing potential.
4. Body Mass Index (BMI) ≤ 45 kg/m²

For inclusion in the optional genetic research, subjects must fulfil the following criterion:

5. Provision of informed consent for genetic research

If a subject declines to participate in the genetic research, there will be no penalty or loss of benefit to the subject. The subject will not be excluded from other aspects of the study described in this Clinical Study Protocol, so long as they consent.

Inclusion criteria before entering long-term, double-blind extension period II (visit 12):

1. Provision of a written informed consent for the participation in the long-term, double-blind extension period II.

3.3.3 Exclusion criteria

Any of the following is regarded as a criterion for exclusion from the study:

Exclusion criteria at randomization visit (visit 2):

1. Clinical diagnosis of type 1 diabetes, MODY or secondary diabetes mellitus (eg chronic pancreatitis, partial pancreatectomy).
2. Symptoms of poorly controlled diabetes that in judgement of the investigator would preclude participation in this trial including, but not limited to, marked polyuria and polydipsia with greater than 10% weight loss during the 3 months prior to enrolment.
3. Treatment with more than two additional OADs
4. History of diabetes insipidus

5. Use of inhaled insulin or injectable GLP-1 receptor agonists or DPP-4 inhibitors within 8 weeks of enrolment visit
6. Calculated Creatinine Clearance <50 ml/min/1.73m² (calculated by Cockcroft-Gault formula) or a measured serum creatinine value of >2 mg/dl (177 μ mol/l). Patients on concomitant metformin therapy will be excluded if serum creatinine ≥ 1.5 mg/dl (133 μ mol/l) for male subjects and ≥ 1.4 mg/dl (124 μ mol/l) for female subjects
7. Known condition of congenital renal glucosuria
8. Total bilirubin >34.2 μ mol/l, >2.0 mg/dl
9. Creatine kinase ≥ 3 xULN
10. Hemoglobin ≤ 10.0 g/dl (≤ 100 g/l) for men; hemoglobin ≤ 9.5 g/dl (≤ 95 g/l) for women
11. Thyroid-stimulating hormone (TSH) values outside normal range confirmed by abnormal T4 values
12. Positive serologic evidence of current infectious liver disease including patients being positive for Hepatitis B viral antibody IgM, Hepatitis B surface antigen and Hepatitis C virus antibody.
13. Any clinically significant abnormality identified on physical examination, ECG or laboratory tests, which in the judgement of the investigator would compromise the patients' safety or successful participation in the clinical study.
14. Significant cardiovascular history within the past 6 months prior to the screening visit, defined as: myocardial infarction, unstable angina pectoris, transient ischemic attack, unstable or previously undiagnosed arrhythmia, cardiac surgery or revascularization (coronary angioplasty or bypass grafts), or cerebrovascular accident
15. Pregnant or breastfeeding patients
16. Treatment with glucocorticoids equivalent to oral prednisolone >10 mg (betametasone >1.2 mg/dexametasone >1.5 mg/hydrocortisone >40 mg)/day within 30 days prior to enrolment; topical or inhaled corticosteroids are allowed
17. History of bariatric surgery
18. Administration of weight loss medication, including but not limited to sibutramine, phentermine, orlistat, rimonabant, benzphetamine, diethylpropion, methamphetamine, and/or phendimetrazine, within 30 days prior to enrolment

19. Treatment for Human immunodeficiency virus (HIV)/use of antiviral drugs (delavirdine, indinavir, nelfinavir, ritonavir, saquinavir) and/or known immunocompromised status, including patients who have undergone organ transplantation
20. Intolerance, contraindication or potential allergy to dapagliflozin or placebo or formulation recipients
21. Congestive heart failure defined as New York Heart Association (NYHA) class III or IV (see [Appendix D](#)), and/or left ventricular ejection fraction of $\leq 40\%$
22. Severe respiratory failure or severe emphysema
23. Severe uncontrolled hypertension defined as systolic BP ≥ 180 mm Hg and/or diastolic BP ≥ 110 mm Hg
24. Patients who, in the judgment of the investigator, may be at risk for dehydration
25. History of chronic hemolytic anemia or hemoglobinopathies (sickle cell anemia or thalassemias, sideroblastic anemia)
26. History of alcohol abuse or illegal drug abuse within the past 12 months
27. History of malignancy within the last 5 years, excluding successful treatment of basal or squamous cell skin carcinoma
28. Involvement in the planning and conduct of the study (applies to both AZ and BMS staff or staff at the study centre)
29. Previous enrolment or randomization to treatment in the present study
30. Received an investigational agent within 30 days prior to receiving study medication
31. Donation or transfusion of blood, plasma or platelets within the past 3 months prior to visit 1
32. Suspected or confirmed poor protocol or medication compliance as judged by the investigator
33. Severe hepatic insufficiency and/or significant abnormal liver function defined as Aspartate aminotransferase (AST) > 3 x upper limit of normal (ULN) and/or Alanine aminotransferase (ALT) > 3 x ULN
34. Urine albumin:creatinine ratio (UACR) > 1800 mg/g (> 203.4 mg/mmol/Cr)

For the participation in the optional genetic research, patients must not

1. Have had previous bone marrow transplant
2. Received blood transfusion in the 120 days preceding the date of genetic sampling collection.

If either of these 2 exclusion criteria is present, the patient cannot participate in the optional blood sample donation.

Exclusion criteria before entering long-term, double-blind extension period II (visit 12):

1. Safety reasons as judged by the investigator, AstraZeneca and/or Bristol-Myers Squibb Pharmacovigilance
2. Severe non-compliance to protocol as judged by the investigator and/or AstraZeneca
3. Any clinical adverse event, laboratory abnormality or intercurrent illness which, in the opinion of the investigator, indicates that continued participation in the study is not in the best interest of the subject
4. Development of study specific discontinuation criteria listed below. These criteria include one or more of the following parameters:
 - (a) Treatment with glucocorticoids equivalent to oral prednisolone >10 mg/day (two temporary periods of higher daily doses but no longer than 7 days each are allowed)
 - (b) Severe hypoglycaemic events, defined as ≥ 1 major hypoglycemia in spite of complete withdrawal of insulin and if applicable other OAD and the investigator decides that current treatment poses the patient at risk of either repeated hypoglycemic events or major hypoglycaemia.
 - (c) Pregnancy identified by positive pregnancy test or otherwise verified
 - (d) Confirmed increase in serum creatinine of ≥ 0.5 mg/dl (44 $\mu\text{mol/L}$) for patients with baseline creatinine of < 1.4 mg/dl (123 $\mu\text{mol/L}$) or confirmed increase in serum creatinine of ≥ 1 mg/dl (88 $\mu\text{mol/L}$) for patients with baseline creatinine of ≥ 1.4 mg/dl (123 $\mu\text{mol/L}$). Patients with serum creatinine above these values will have their study medication held and a repeated serum creatinine test within 7 days. If serum creatinine is still elevated as specified above (≥ 0.5 mg/dl or ≥ 1.0 mg/dl above baseline), the patient should discontinue the clinical study medication. Otherwise study medication may be resumed unless otherwise contraindicated. For further details please see [Appendix G](#) of this protocol.
 - (e) CK >10 x ULN confirmed at a repeated measurement within 24 hours.

- (f) Patients with a central laboratory ALT and/or AST >3x ULN will be scheduled for a follow-up visit within 3 calendar days following the receipt of the result. See [Appendix H](#) for further guidance.

Patients should be discontinued from study if the initial and repeat laboratory tests meet any of the following criteria:

- ALT and/or AST are >3x ULN and TB>1.5x ULN
- ALT and/or AST are >5x ULN for ≥ 14 consecutive days, at any time after initial confirmatory results
- ALT and/or AST are >8x ULN

- (g) No longer applicable.

- (h) Serum sodium ≤ 125 mmol/l with or without symptoms: dosing of blinded study medication will be interrupted. For further detail please follow instructions stated in [Appendix E](#).

- (i) Haemoglobin ≤ 9.0 g/dl (90 g/l)

3.3.4 Restrictions

After visit 1 all patients will visit the clinic on a fasting stomach in the morning, before 11 a.m. if possible. Patients will be instructed to abstain from all food and beverages for 12 hours prior to each visit at the clinic (drinking water is allowed). Allowed medications can be taken with water only.

The patients should refrain from alcohol intake 24 hours prior to each visit and are recommended not to use tobacco/nicotine within 12 hours prior to each visit.

If a patient comes to a visit without having followed the above instructions, then the patient will be re-scheduled for the entire visit (if possible within allowed time-window, see [Table 2](#)).

As up to approximately 378 ml of blood will be drawn from the patients during the entire duration of the Clinical Study, patients should be instructed to abstain from donating any blood during the Clinical Study and for 3 months following their last study visit.

Restricted concomitant medications are listed in section [3.7](#), and fasting prior to laboratory assessments are detailed in section [4.7.2.1](#).

3.3.5 Discontinuation of subjects from treatment or assessment

3.3.5.1 Criteria for discontinuation

The study may be terminated at individual centres if the study procedures are not being performed according to GCP or if recruitment is slow. AstraZeneca may also terminate the entire study prematurely if concerns for safety arise within this study or in any other study with dapagliflozin.

Patients may be discontinued from study treatment and assessments at any time. Specific reasons for discontinuing a patient are:

1. Voluntary discontinuation by the patient who is at any time free to discontinue his/her participation in the study, without prejudice to further treatment
2. Safety reasons as judged by the investigator, AstraZeneca and/or Bristol-Myers Squibb Pharmacovigilance
3. Severe non-compliance to protocol as judged by the investigator and/or AstraZeneca
4. Incorrect enrolment i.e., the patient does not meet the required inclusion/exclusion criteria for the study
5. Any clinical adverse event, laboratory abnormality or intercurrent illness which, in the opinion of the investigator, indicates that continued participation in the study is not in the best interest of the subject.
6. Patient lost to follow-up (as defined by the inability to reach the patient after 3 documented phone calls, fax, email, or attempts to contact him/her through patient locator agencies (if allowed per national regulation) and having sent one letter by registered/certified mail; all should be documented in the patient's medical records).
7. Development of study specific discontinuation criteria listed below. These criteria include one or more of the following parameters:
 - (a) Treatment with glucocorticoids equivalent to oral prednisolone >10 mg/day (two temporary periods of higher daily doses but no longer than 7 days each are allowed)
 - (b) Severe hypoglycaemic events, defined as ≥ 1 major hypoglycemia in spite of complete withdrawal of insulin and if applicable other OAD and the investigator decides that current treatment poses the patient at risk of either repeated hypoglycemic events or major hypoglycaemia.
 - (c) Pregnancy identified by positive pregnancy test or otherwise verified

- (d) Confirmed increase in serum creatinine of ≥ 0.5 mg/dl (44 $\mu\text{mol/L}$) for patients with baseline creatinine of < 1.4 mg/dl (123 $\mu\text{mol/L}$) or confirmed increase in serum creatinine of ≥ 1 mg/dl (88 $\mu\text{mol/L}$) for patients with baseline creatinine of ≥ 1.4 mg/dl (123 $\mu\text{mol/L}$). Patients with serum creatinine above these values will have their study medication held and a repeated serum creatinine test within 7 days. If serum creatinine is still elevated as specified above (≥ 0.5 mg/dl or ≥ 1.0 mg/dl above baseline), the patient should discontinue the clinical study medication. Otherwise study medication may be resumed unless otherwise contraindicated. For further details please see [Appendix G](#) of this protocol.
- (e) CK >10 x ULN confirmed at a repeated measurement within 24 hours.
- (f) Patients with a central laboratory ALT and/or AST >3 x ULN will be scheduled for a follow-up visit within 3 calendar days following the receipt of the result. See [Appendix H](#) for further guidance.
- Patients should be discontinued from study if the initial and repeat laboratory tests meet any of the following criteria:
- ALT and/or AST are >3 x ULN and TB >1.5 x ULN
 - ALT and/or AST are >5 x ULN for ≥ 14 consecutive days, at any time after initial confirmatory results
 - ALT and/or AST are >8 x ULN
- (g) No longer applicable
- (h) Serum sodium ≤ 125 mmol/l with or without symptoms: dosing of blinded study medication will be interrupted. For further detail please follow instructions stated in [Appendix E](#).
- (i) Haemoglobin ≤ 9.0 g/dl (90 g/l).

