3.3.5.2 Procedures for discontinuation

Patients who discontinue should always be asked about the reason(s) for their discontinuation and the presence of any adverse events. If possible, they should be seen and assessed by an investigator(s). Adverse events should be followed up; diary cards and investigational products should be returned by the patient.

Patients with an increased CK >10 x ULN will have their study medication held and repeated CK test within 24 hours. If repeated CK is still >10 x ULN the patient should discontinue the study medication. Otherwise study medication may be resumed unless otherwise contraindicated.

Patients with increased liver function tests as defined in section 3.3.5.1 under listings 7(f), will be scheduled for a follow-up visit within 3 calendar days following the receipt of the result. Patients should remain on study medication until the confirmatory results are obtained unless otherwise contraindicated. See CSP [Appendix H - Algorithm on Management of Sustained Elevated Liver Safety Abnormalities](#) for further guidance. If repeated liver function tests still are increased as outlined in section 3.3.5.1 under listings 7(f), the patient should permanently discontinue all study medication and be withdrawn from the study (see CSP [Appendix H - Algorithm on Management of Sustained Elevated Liver Safety Abnormalities](#) for further guidance).

Randomized patients who discontinue before week 104 should complete the procedures described for Visit 18 as soon as possible but at the latest 7 days after discontinuation. These patients should also be scheduled for a follow-up visit (i.e. procedures of Visit 19) 3 weeks after discontinuation of investigational product.

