3.3.5.4 Procedures for handling incorrect enrolled subjects

Patients not meeting the inclusion/exclusion criteria for the study should, under no circumstances, be randomized into the study. If a patient not meeting the study criteria is randomized in error, the patient should complete the study unless there are safety concerns or if the patient withdraws the consent. Data collected for patients randomized in error will be included in the analyses.

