6.3.1 Full analysis set

The full analysis set will include all randomized subjects (as randomized) who received at least one dose of study medication during the 24-week double-blind treatment period, who have a non-missing baseline value and at least one post-baseline efficacy value for at least one efficacy variable during the 24-week double-blind treatment period. The intention-to-treat principle will be preserved despite the exclusion of subjects who took no study medication, as the decision of whether or not to begin treatment during the randomized treatment period could not be influenced by knowledge of the assigned treatment. Missing values will be replaced by the last observation carried forward (LOCF) approach.

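### Section 3.3.5.1 lets a site stop a randomised patient for ineligibility alone, while section 3.3.5.4 says that patient should complete the study, and neither refers to the other

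*Protocol*

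**What the plan says.** Section 3.3.5.1 of the protocol opens its list of stopping grounds with "Patients may be discontinued from study treatment and assessments at any time. Specific reasons for discontinuing a patient are". Reason 4 on that list is "Incorrect enrolment i.e., the patient does not meet the required inclusion/exclusion criteria for the study". Reason 1 is voluntary discontinuation by the patient and reason 2 is safety.

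Section 3.3.5.4, headed "Procedures for handling incorrect enrolled subjects", first forbids randomising anyone who fails the criteria. It then says that if this happens in error, "the patient should complete the study unless there are safety concerns or if the patient withdraws the consent". It adds: "Data collected for patients randomized in error will be included in the analyses".

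Section 3.3.5.2 sets out what follows a stop: "Randomized patients who discontinue before week 104 should complete the procedures described for Visit 18", within 7 days at the latest, and "These patients should also be scheduled for a follow-up visit (i.e. procedures of Visit 19) 3 weeks after discontinuation of investigational product". It requires no further scheduled visits. Section 6.3.1 says of the full analysis set: "Missing values will be replaced by the last observation carried forward (LOCF) approach".

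**The concern.** The two sections give different answers for the same patient: randomised, later found not to have met an entry criterion, safe on treatment and willing to continue. Section 3.3.5.1 permits a stop; section 3.3.5.4 says the patient should go on to the end.

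The consequence is discretionary loss of data after randomisation. A patient stopped under reason 4 before week 24 would normally stay in the full analysis set, but the primary value would be carried forward rather than observed. That works against section 3.3.5.4, which sets out to keep these patients and their data. With about 150 centres, different sites can handle the same situation differently, and each could cite the protocol in support. The same wording applies through week 104, so it also touches the long-term safety data for which extension period II was added.

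**Working it through.** **Comparing the two rules for a randomised patient**

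| Situation | 3.3.5.1 | 3.3.5.4 |
|---|---|---|
| Ineligible, safety concern | May stop (reason 2) | Exception: need not complete |
| Ineligible, withdraws | May stop (reason 1) | Exception: need not complete |
| Ineligible, safe and willing | May stop (reason 4) | Should complete |

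The first two rows agree without any help from reason 4. Unless another listed ground applies, reason 4 changes the outcome only in the third row, where it conflicts with section 3.3.5.4.

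**Looking for text that settles precedence.** Section 3.3.5.1 refers only to Appendices E, G and H. Section 3.3.5.4 contains no cross-reference. Section 3.3.5.2 points back to section 3.3.5.1 only for item 7(f), the liver tests. Nothing says which rule governs.

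**Reproducing the planning figures (section 6.5).** Inputs: difference 0.5%, SD 1.2%, two-sided alpha 0.019, power 90%, 5% not evaluable.

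- The normal approximation gives 152 per group. The noncentral t gives 153 as the smallest size reaching 90% (power 0.9001; 0.898 at 152). The stated 153 reproduces.
- 153/0.95 = 161.05, stated as 161; 4 × 161 = 644.

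**Illustrating the size.** Let f be the fraction stopped under reason 4 and suppose, as a worst case, that their carried-forward values retain none of the 0.5% effect. The protocol gives no value for f; 1–5% is an assumption. The SD is held at 1.2. Then

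- d = 0.5 × (1 − f)
- power = Φ( d / (1.2 × √(2/n)) − z), with z = z(1 − 0.019/2)

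For the trial as recruited, evaluable patients per arm = 808/4 × 0.95 = 191.9, taken as 192.

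| f | d | Power, n = 153 | Power, n = 192 |
|---|---|---|---|
| 0 | 0.500 | 0.903 | 0.959 |
| 1% | 0.495 | 0.897 | 0.955 |
| 5% | 0.475 | 0.868 | 0.937 |

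**The case against.** The strongest reply is that the two sections can be read together. Section 3.3.5.1 is a general, permissive list. Section 3.3.5.4 is a specific instruction a little later under the same parent heading, and a specific rule ordinarily limits a general permission. Reason 4 also has a natural use elsewhere: in this protocol enrolment is visit 1 and randomisation is visit 2, and about 1610 patients were to be enrolled to randomise 644. Incorrect enrolment could therefore mean the 1610 − 644 = 966 or so who would never be randomised. The visit 12 exclusion list in section 3.3.3, which concerns only randomised patients, repeats several of the discontinuation grounds but not this one.

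That reading is available, but the text does not compel it. The list governs stopping study treatment, which begins only at randomisation. Reason 4 carries no time limit, and the heading of section 3.3.5.4 uses nearly the same term for a section that covers patients randomised in error. The visit 12 list is weak evidence: it also omits voluntary withdrawal and loss to follow-up, and footnote j to Table 1 excludes at visit 12 any patient with discontinuation criteria present, which on its face would include reason 4. A careful reader may well prefer section 3.3.5.4, but sites should not have to infer that.

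The objections about size largely stand. A stopped patient has an HbA1c at the end-of-treatment visit, and HbA1c is also measured at weeks 1, 4, 8, 12, 16 and 20, so LOCF would usually carry forward a value with some effect in it. Sites are blinded to allocation, and no bias between arms is shown. Since 808 patients had already been randomised when this edition was written, a change in wording helps only those still on treatment.

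**Conclusion.** The inconsistency is real. For a randomised, ineligible, safe and willing patient, one section permits a stop and the other calls for completion, with nothing to rank them. Following reason 4 produces avoidable loss after randomisation, with LOCF in place of a week-24 HbA1c that could have been observed, provided insulin had not been up-titrated (section 6.4.1 uses the last value before up-titration in any case).

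The effect is probably small and cannot be sized from the protocol. Under the assumed 1–5% and complete loss of effect, power falls by at most 0.903 − 0.868 = 0.035 at the planned size, and stays at 0.937 or above at the size actually randomised. The case for correction rests on the contradiction and the avoidable data loss, not on power. It should be corrected, but it does not threaten the primary analysis.

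**What to change.** Delete reason 4 from section 3.3.5.1, or limit it to patients found ineligible before randomisation or with a safety concern. Add a cross-reference naming section 3.3.5.4 as the governing rule for patients randomised in error.

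This is a one-line text change in an amendment. It adds no visits or procedures, and the planned analyses are unchanged.
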